8.3 Investigational Product (Study Drug)

8.3.1 Treatments Administered

8.3.1.1 During Study Period

In Part A of the study each subject will receive a total of 2 single doses of the study drug administered as a SC injection into the abdominal area over the 12 month study period. The 2 injections of the study drug will be at 6-month intervals: one at Baseline (Day 0) and one at the Month 6 visit (24 weeks).

If Part B extension is conducted, then subjects will receive 2 additional SC administrations of the study drug at 5-month intervals: one at the Month 11 visit and one at the Month 16 visit.

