9.2.6 Safety Analyses

A listing of all AEs, including SAEs and events leading to discontinuation, will be provided. The Data Management team will compile a list of all AEs based on the information entered in the eCRF. This listing will be sent to TOLMAR and the CRO Safety Department for the proper reconciliation of the study and safety databases. These listings will include: event term as reported, event term as coded with the Medical Dictionary for Regulatory Activities (MedDRA version(s) will be documented in the final Clinical Study Report), start date, start time (only for events beginning on the day of the first injection), stop date, outcome, seriousness, severity, relationship to Investigational Product, and action taken with Investigational Product. AEs recorded after signing of the ICF/Assent but PRIOR to the first injection will be reported as non-TEAEs.

The number and percent of subjects reporting AEs will be tabulated. Summaries will be presented by body system organ class (SOC) and preferred term (PT), and further by severity and relationship to the study drug.

SAEs will be discussed within the clinical study report. Data collected pertaining to SAEs will be presented in data listings.

Continuous serum chemistry and hematology laboratory results will be summarized using mean, standard deviation, median, minimum, and maximum for each study visit, each cohort and each treatment cycle with each cohort. Urinalysis results by dipstick will be listed. Laboratory test results that are normal at Screening and become abnormal during treatment will be reported.

Vital signs will be summarized at each time point with mean, standard deviation, median, minimum, and maximum by each cohort and each treatment period with each cohort.

Other medical history data and the physical examination data will be tabulated.

Concomitant medications will be classified according to the World Health Organization (WHO) Drug Dictionary (version(s) will be documented in the final Clinical Study Report) and will be presented in data listings.

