## 12. IMPUTATION AND MISSING DATA

Unless otherwise indicated, imputation of missing data will not be performed for baseline, efficacy and safety variable values. Each table containing an analysis that reflects an outcome at a given time point in the study will contain only subjects in the analysis population under examination who have data available at that time point.

If a missing concentration datum is surrounded by non-missing values, interpolation will be used in the calculation of AUC, Cmax and Tmax. Otherwise, the nearest non-missing point in time will be used.

If missing date and time values are evident in data not used to develop PK parameters, the following missing date and time algorithm may be applied.

For partial start date/time:

- If the year is unknown, then the date will not be imputed and will be assigned a missing value.
- If the month is unknown, then:
  - If the year matches the year of the dose of study drug date, then the month and day of the dose of study drug date will be imputed.
  - Otherwise, 'January' (01) will be assigned.
- If the day is unknown, then:
  - If the month and year match the month and year of the dose of study drug date, then the day of the dose of study drug date will be imputed.
  - Otherwise, '01' will be assigned.
- If the day is unknown, then:
  - If the month and year match the month and year of the dose of study drug date, then the day of the dose of study drug date will be imputed.
  - Otherwise, '01' will be assigned.
- If the time is unknown, then:
  - If the date (day, month, and year) matches the date of the dose of study drug date, then the time of the dose of study drug time will be imputed.
  - Otherwise, '00' will be assigned.
- For partial stop date/time:
  - If the year is unknown, then the date will not be imputed and will be assigned a missing value.
  - If the month is unknown, then 'December' (12) will be assigned.
  - If the day is unknown, then the last day of the month will be assigned.
  - If the time is unknown, then the last time of the day will be assigned.

If time to an event were needed when only the hour, and not the minutes, are reported for the time of the event, then the minutes will be set to zero.

Any deviations from the implementation of the missing date and time algorithms will be documented in the dataset documentation and final report.

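### SAP 12 imputes a partial start date to the dose date without checking the recorded stop date, so a record that ended before Injection #1 can start after its own stop

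*SAP*

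**What the plan says.** SAP 12 introduces its partial-date rules, for data not used to derive PK parameters, with permissive wording: "the following missing date and time algorithm may be applied". For a start date with the day unknown, the condition is "If the month and year match the month and year of the dose of study drug date" and the action is "then the day of the dose of study drug date will be imputed"; otherwise the first of the month is used. This bullet is printed twice. With the month unknown, the rule is "If the year matches the year of the dose of study drug date, then the month and day of the dose of study drug date" are imputed; otherwise January is assigned. Partial stop dates have their own rule, for example "If the day is unknown, then the last day of the month will be assigned". No start-date bullet refers to the stop date.

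The rule speaks of one dose. Protocol 8.3.1.1 gives more: in Part A "each subject will receive a total of 2 single doses of the study drug", and if Part B is conducted "subjects will receive 2 additional SC administrations of the study drug at 5-month intervals".

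Treatment emergence turns on the first injection. Protocol 9.2.6 states that AEs recorded after consent or assent but "PRIOR to the first injection will be reported as non-TEAEs". Protocol 8.5.1 treats non-serious AEs that occur in that interval in the same way, and step 11 of Protocol 8.6.2 has them recorded at Visit 1 before dosing. SAP 14.4 plans an individual listing of TEAEs and a separate listing of AEs that are not treatment-emergent.

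**The concern.** Imputing an unknown start to the dose date is a common cautious convention: in doubt, the event counts as on treatment. It is cautious only while real doubt remains. A complete stop date before the dose removes the doubt, and the rule ignores it. The result is a start later than the stop, which is impossible, and a start on the injection day for something already over.

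The separate TEAE and non-TEAE listings need every AE classified, yet the SAP gives no date-based definition of a TEAE, and SAP 12 is its only rule for partial dates. A programmer who flags on start date would move such an event to the wrong listing. Separately, when only the year of a start is known, the text does not say which injection is meant, so two programmers could derive different dates from the same record.

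**Working it through.** The plan states no figure on this point, so there is none to reproduce. The check applies the rule as written.

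**Inputs**
- Start-date and stop-date rules: SAP 12.
- Injections at Weeks 0 and 24, and at Weeks 44 and 64 if Part B is invoked; visits after Day 0 have a window of ±7 days: Protocol Tables 1 and 3.
- Screening of up to 28 days: Protocol Synopsis.
- Assumed: calendar dates equally likely; a full stop date is recorded; the start day is missing.

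**Worked case.** First dose 20 March; start March, day unknown; stop 10 March.
- SAP rule: month and year match, so start = 20 March. Stop minus start = 10 − 20 = −10 days.
- If only the year of the start is known, the year matches and the start is again 20 March.
- With a stop-date check: the stop is before the dose, so start = 1 March (day unknown) and the event stays pre-treatment.

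The time bullet in SAP 12 adds to this. A record moved to the dose date with no start time is given the dose time.

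**How often the rule misdates such a record, given that one exists.** All 365 first-dose dates were enumerated, with starts 1 to W days before the dose and every stop from the start to the day before the dose, equally weighted. The number of cases is 365 × W(W+1)/2.

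| W (days) | Cases | Start imputed to the dose date | Share | With stop-date check |
|---|---|---|---|---|
| 7 | 365 × 28 = 10,220 | 8,540 | 83.6% | 0 |
| 14 | 365 × 105 = 38,325 | 26,145 | 68.2% | 0 |
| 28 | 365 × 406 = 148,190 | 55,622 | 37.5% | 0 |

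In every misdated case the imputed start is after the recorded stop. These are shares of records that ended before dosing and lack a start day, not shares of all AEs.

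**Which dose is meant**
- Same month: nominal gaps are 24 × 7 = 168, 20 × 7 = 140 and 140 days. The smallest gap with both windows used is 140 − 7 − 7 = 126 days, longer than any month. At most one injection falls in a calendar month, so the day-unknown bullet never has two matches.
- Same year: both Part A injections fall in one calendar year for (365 − 168)/365 = 197/365 = 54.0% of first-dose dates. The Week 24 window gives (365 − 175)/365 = 52.1% to (365 − 161)/365 = 55.9%.
- With Part B, Weeks 0 to 44 span 308 days, so three injections can share a year. Weeks 0 to 64 span 448 days, so four cannot.
- Effect: every later injection follows Injection #1, so choosing one of them changes the imputed date but not treatment emergence.

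**The case against.** The strongest reply is that no harm is shown. The algorithm is optional, and SAP 12 requires departures from it to be documented. The protocol classifies AEs by whether they occurred or were recorded before the first injection, and Visit 1 has a pre-dose step for this. The event in the worked case would normally already stand there as non-treatment-emergent, and only one reported late would depend on dates. Neither document ties the TEAE flag to an imputed date. Protocol 10.4 and 10.5 require source verification and complete eCRF fields, so few such records should survive.

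All of this limits the consequence. It does not repair the rule: an option with no criterion for its use gives a programmer no reason to depart from it, and followed literally it yields an impossible date.

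Four stronger readings are tempting, and the documents do not support them.
- *TEAE percentages are inflated.* SAP 14.4 and Protocol 9.2.6 tabulate subjects reporting AEs. TEAE status is named for listings, so a flipped flag moves a row between listings and leaves the planned percentages unchanged.
- *Prior medications become concomitant.* SAP 14.2.2 summarises both and gives no date rule to separate them. Under a rule based on stop date, a drug stopped before dosing would still be prior.
- *False acute reactions appear on injection days.* Acute reactions are analysed from the symptom questionnaire (Protocol 8.5.1 and 9.2.2, SAP 8.2.3), not from AE onset dates.
- *Not knowing which dose applies alters emergence.* Emergence turns on Injection #1, so an event in the month of a later injection is treatment-emergent whatever day is imputed.

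**Conclusion.** The point holds as a defect in a data-handling rule. For an event or medication that ended before Injection #1 in the same month, or in the same year when the month is unknown, SAP 12 as written gives a start later than the recorded stop. If the TEAE flag is built on start date, which is an assumption because the SAP does not say, such an AE could be listed as treatment-emergent, contrary to Protocol 8.5.1 and 9.2.6. Separately, the month-unknown bullet has no unique answer whenever two or more injections share a calendar year.

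The importance is low. The documents give no count of partial dates; that few records are affected is a judgement, resting on the short screening period and the planned data checks. The effect is mainly on the TEAE and non-TEAE listings and on dates in the analysis datasets. The LH endpoint is not affected.

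**What to change.** Amend SAP 12 as follows:

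1. An imputed start date may not be later than the recorded stop date.
2. The reference dose for both the day-unknown and the month-unknown bullets is Injection #1.
3. Impute to that dose date only when the stop date is missing or falls on or after it. Otherwise use the first day of the known month, or of the known year when the month is missing. For AEs, use the consent date instead if it is later than that day and not after the stop date.
4. Delete the duplicated day-unknown bullet.

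Item 2 also settles the month-unknown ambiguity. A start known only to lie in a later year than Injection #1 goes to 1 January of that year, which is still after Injection #1. The cost is a few sentences in the SAP and minor programming, with no change to data collection.

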8.5 Safety Evaluation

8.5.1 Safety Parameters

Safety parameters to be measured/assessed include eligibility assessments, medical history, vital signs, physical examinations, clinical laboratory tests, and pregnancy tests. Any abnormal hematology, serum chemistry, serum lipid, or urinalysis parameters considered clinically significant by the Investigator will be captured as AEs.

Subjects will be monitored throughout the study for AEs, as well as for changes in clinical status, vital signs, and laboratory data. Any non-serious AEs occurring from the time the ICF and Assent forms, if required, are signed until just prior to receiving the first injection of study drug will be considered as non-TEAEs unrelated to study drug administration.

Serious adverse events (SAEs) that occur as a result of study-mandated procedures during the time period after the ICF and Assent forms are signed, as appropriate, but prior to receiving the first injection of study drug will be collected but not designated as TEAEs.

In order to evaluate changes in the acute (within two weeks of administration) and chronic hormonal responses associated with GnRH antagonist treatments over time, subjects (or their parents/guardians) will be asked two weeks (14 days \pm 2 days) after every study drug administration (by telephone contact), and at each scheduled visit, the following question(s):

- How have you felt in the last two weeks?

or alternatively (if the parent or guardian is answering on behalf of the subject)

- How has your child felt in the last two weeks?

Investigators will record any adverse events that are reported at that time.

In addition the investigators will categorize the more specific responses that have been identified in the table ([Table 4](#)), which are often associated with GnRH antagonist injectable treatments. If the subject (or parent/guardian) does not report any condition (within the last two weeks) that fits into the [Table 4](#) categories, the Investigator will check the response that no conditions associated with GnRH antagonists were reported (“NO”). If any of the conditions reported by the subject (or parent/guardian) fit into one (or more) of the categories, then the Investigator will check “YES” for each applicable category. This reported information will be collected by completing [Table 4](#):

Table 4 GnRH Antagonist Evaluations

Any GnRH antagonist conditions reported?	Yes/No
If the answer is “Yes”, please categorize as described below:	

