8.5.5 Reporting of Adverse Events

All AEs that are observed by the Investigator or one of his/her medical collaborators, or reported by the subject, will be reported even if they are potentially attributable to unrelated medical

conditions or other medications the subject may be taking. The information recorded for AEs will include start date, a description of the AE, severity, causal relationship to Investigational Product/study drug, action taken, outcome of the event (including any treatment and/or hospitalization), and stop date. In addition, start time will be collected for events beginning on the day of the first injection.

Medical conditions or diseases present before a subject is enrolled in the study are only considered AEs if they worsen after the subject is enrolled.

For each AE, the seriousness, severity, and causal relationship to study drug will be assessed and entered in the source document. All items on the AE page of the eCRF should be completed for each AE.

Surgical procedures themselves are not AEs; they are therapeutic measures for conditions that require surgery. The condition for which the surgery is required is an AE, if it occurs or is detected during the study period. Planned surgical measures and the conditions leading to these measures are not AEs, if the condition(s) was (were) known before the study treatment. In the latter case, the condition should be reported as medical history.

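### SAP section 12 sets an hour-only event time to the start of the hour without checking the dose time, so a reaction soon after the first injection can be timed before it

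*SAP*

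**What the plan says.** SAP section 12 introduces its conventions for incomplete dates and times, outside the PK data, with "the following missing date and time algorithm may be applied". For a start time that is wholly unknown on a date matching a dose date, "then the time of the dose of study drug time will be imputed". The start rules for an unknown month or day follow the same pattern: where the known part matches the dose date, the dose date fills the gap.

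The section also has a separate sentence for a time reported by hour alone. It applies on the condition that a time to event is needed, and it says that "when only the hour, and not the minutes, are reported for the time of the event, then the minutes will be set to zero". It does not refer to the dose.

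On collection, Protocol 8.5.5 states: "In addition, start time will be collected for events beginning on the day of the first injection". Protocol 9.2.6 confirms that start time is listed for that day only. On classification, Protocol 9.2.6 says that AEs recorded after consent but "PRIOR to the first injection will be reported as non-TEAEs". Protocol 8.5.1 says that non-serious events in that window "will be considered as non-TEAEs unrelated to study drug administration". Dose times are recorded at the site (Protocol 8.3.4.2), so the two clock times can be compared.

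**The concern.** Among the start-side imputations in SAP section 12, the hour-only rule is the only one that does not look at the dose. As a result, a record with more information can be placed worse than a record with none. An event with no time on the dosing date is put at the injection. The same event with its hour known can be put before the injection.

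The rule matters most on the first-injection day, for the reasons given by the collection and classification rules above. Early reactions are the most exposed, because they are the most likely to share a clock hour with the injection. The protocol names injection-site burning or stinging, pain and allergic reactions among the conditions to be asked about (Table 4). At stake is a negative time from dose for such an event and, if that time is used for classification, its place in the listing of non-treatment-emergent events instead of the TEAE listing.

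**Working it through.** The plan gives no figure on this point, so there is none to reproduce. The check is how often the rule puts a truly post-dose event before the dose.

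**Inputs**
- Rule: an hour-only time becomes HH:00 (SAP 12).
- Comparison: imputed event time against recorded dose time (Protocol 8.3.4.2), first injection only (Protocol 8.5.1 and 9.2.6).
- Assumption, not in the documents: the injection minute m is uniform over 0 to 59. Alternative assumption: injections fall only on quarter hours.

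**Formula.** Let the injection be at minute m and the true onset T whole minutes later. The imputed time precedes the dose when the onset is in the same clock hour (m + T < 60) and the injection is not exactly on the hour (m > 0). For T from 0 to 59, that is m = 1 to 59 − T, so the share is (59 − T)/60.

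| Onset after injection | Uniform minute | Quarter hours only |
|---|---|---|
| 1 min | 58/60 = 97% | 3/4 = 75% |
| 5 min | 54/60 = 90% | 3/4 = 75% |
| 10 min | 49/60 = 82% | 3/4 = 75% |
| 15 min | 44/60 = 73% | 2/4 = 50% |
| 30 min | 29/60 = 48% | 1/4 = 25% |
| 45 min | 14/60 = 23% | not run |
| 59 min or later | 0% | not run |

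**Examples**
- Injection 10:20, onset 10:25, recorded as hour 10: imputed 10:00, before the dose.
- Injection 10:00, onset 10:05: imputed 10:00, not before the dose.
- Injection 10:55, onset 11:02: imputed 11:00, not before the dose.

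These shares are conditional on the minutes being missing. The documents do not say how often that will happen, so the shares cannot be turned into a number of children.

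**Check of the fix.** Use the dose time when the reported hour equals the injection hour on that date. Over 60 injection minutes and onsets of 0 to 119 minutes (60 × 120 = 7,200 combinations), no post-dose event falls before the injection. In the first example the event moves to 10:20.

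**Cost of the fix.** The current rule never misplaces a truly pre-dose event, because rounding down keeps it before the dose. Under the fix, without any exception, an hour-only event that began 5 minutes before dosing would count as treatment-emergent in 55/60 = 92% of cases. The exception for records showing pre-dose onset is therefore needed.

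**The case against.** The strongest reply is that the rule may never operate. It applies only where a time to event is needed, and SAP section 7 with Table 5 plans no time-to-event analysis of AEs. The algorithm is worded as optional. No sentence in either document says that the rule decides treatment-emergent status, and the SAP gives no clock-time definition of a TEAE. All of this stands. Two things limit it. Section 12 requires deviations from the algorithm to be documented, which treats it as the default. With no time-to-event analysis planned, onset relative to dose is the most foreseeable use of the sentence.

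The second reply is that the sites already separate the events. Protocol 8.6.2 has pre-dose AEs recorded before the injection and a further AE assessment afterwards. Start time is required that day, children stay in clinic for sampling to 6 hours, and entries are queried and source-verified. This also stands, and it makes hour-only records less likely and easier to resolve. It does not tell the programmer what to do with one.

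A reader might go further and infer that the rule turns an immediate reaction into an unrelated event and drops it from the treatment-emergent tables; two such records among 60 children would be 2/60 = 3.3 percentage points. The documents do not support that:
- SAP 14.4 and the Table 5 footnote tabulate AEs in the Safety population without restricting them to TEAEs. The TEAE split appears in the listings.
- Protocol 8.5.5.2 has causality rated for every AE, whatever time is imputed. The wording in Protocol 8.5.1 on unrelatedness covers non-serious pre-dose events only.
- Injection-site and allergic symptoms are also captured by the Table 4 questions, which use no clock time.
- Reactions to injections 2 to 4 are after the first dose in any case.

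**Conclusion.** The point holds as a small internal inconsistency in SAP section 12. A stated rule can give a negative time from dose to an event that began after the first injection in the same clock hour, while the neighbouring rule for a wholly unknown time prevents this. Among hour-only records, about 90% with onset at 5 minutes and 48% with onset at 30 minutes would be misplaced if the injection minute is uniform over the hour. On quarter-hour injections the shares are 75% and 25%.

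The move to the non-treatment-emergent listing depends on one further condition, that the imputed time is used to derive treatment-emergent status. The SAP neither says so nor rules it out. The count of affected records is unknown and probably small. No fall in AE incidence and no change in causality rating is established, and the primary LH endpoint is untouched. It is a minor point, worth correcting because the correction is nearly free.

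**What to change.** Replace the hour-only sentence in SAP section 12 with: *If only the hour is reported and it equals the hour of the study drug injection on that date, the dose time is imputed unless the record (including pre-dose AE collection at Visit 1) shows the event began before dosing; otherwise minutes are set to zero.*

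This extends the section's own dose-matching convention to hour-only times. It works whether or not the imputed time is later used for treatment-emergent status. The cost is one sentence and one line of code. The downside is that a few true pre-dose events in the injection hour may be counted as treatment-emergent where the record is silent, which is the direction the SAP already takes for unknown times.
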